#### 7.1.4. Serious Adverse Events

Serious adverse events will be identified and captured as SAEs if AEs met the definitions of SAE specified in the study protocol. Serious adverse events captured and stored in the clinical database will be reconciled with the SAE database from the Gilead Drug Safety and Public Health Department before database finalization.

#### 7.1.5. Treatment-Emergent Adverse Events

##### 7.1.5.1. Definition of Treatment-Emergent

Treatment-emergent adverse events (TEAEs) are defined as one or both of the following:

- Any AEs with an onset date on or after the study drug start date and no later than 30 days after permanent discontinuation of study drug.
- Any AEs leading to premature discontinuation of study drug.

#### 7.1.5.2. Incomplete Dates

If the onset date of AE is incomplete, then the month and year (or year alone if month is not recorded) of onset determine whether an AE is treatment emergent, as long as the AE stop date is not prior to the first dose date of study drug. The event is considered treatment emergent if both of the following 2 criteria are met:

- The AE onset and end dates are the same as or after the month and year (or year) of the first dose date of study drug
- The AE onset date is the same as or before the month and year (or year) of 30th day after the date of the last dose of study drug

An AE with a completely missing onset and stop dates, or with the onset date missing and a stop date later than the first dose date of study drug, will be considered to be treatment-emergent.

#### 7.1.6. Summaries of Adverse Events and Deaths

A brief high-level summary of TEAEs will be provided by the number and percentage of subjects who had the following: any AE, any AE of Grade 3 or above, any AE of Grade 2 or above, any treatment-related AE, any treatment-related AE of Grade 3 or above, any treatment-related AE of Grade 2 or above, any SAE, any treatment-related SAE, and any AE that led to premature discontinuation of LDV/SOF, and any AE that led to interruption of LDV/SOF. All deaths (including those that are treatment emergent and those that are not treatment emergent) observed during the study will also be summarized and included in this table.

Adverse event summaries will provide the number and percentage of subjects with TEAEs by SOC and PT based on the safety analysis set as follows:

- All AEs
- AEs of Grade 3 or above
- AEs of Grade 2 or above
- All treatment-related AEs
- Treatment-related AEs of Grade 3 or above
- Treatment-related AEs of Grade 2 or above
- All SAEs
- All treatment-related SAEs
- AEs leading to premature discontinuation of LDV/SOF
- Adverse Events Leading to Interruption of LDV/SOF

Multiple events will be counted once only per subject in each summary. Adverse events will be summarized and listed in alphabetic order of SOC and then by PT in order of descending incidence within each SOC. In summaries by severity grade, the most severe grade will be used for those AEs that occurred more than once in an individual subject during the study.

In addition to the above summary tables, TEAEs will also be summarized by PT only, in order of descending incidence for:

- All AEs
- AEs that occurred in at least 5% of subjects
- AEs of Grade 3 or above
- All treatment-related AEs
- All SAEs
- AEs leading to premature discontinuation of LDV/SOF
- AEs leading to interruption of LDV/SOF

In addition to the summaries described above, data listings will be provided for the following:

- All AEs
- AEs of Grade 3 or above
- SAEs
- Deaths
- AEs leading to premature discontinuation of LDV/SOF
- AEs leading to interruption of LDV/SOF
- AE with changes other than resolution dates between the SVR12 and SVR24 analyses (provided only at the final analysis)

All deaths (including those that are treatment emergent and those that are not treatment emergent) observed during the study will also be summarized.

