2. OBJECTIVES

The primary objectives of this study are as follows:

- To evaluate the antiviral efficacy of treatment with LDV/SOF for 8,12, or 24 weeks in subjects with chronic hepatitis C virus (HCV) infection who are on dialysis for ESRD, as measured by the proportion of subjects with sustained viral response 12 weeks after cessation of treatment (SVR12)
- To evaluate the safety and tolerability of each treatment regimen

The secondary objectives of this study are as follows:

- To determine the proportion of subjects who attain SVR at 4 and 24 weeks after cessation of each study treatment regimen (SVR4 and SVR24)
- To evaluate the proportion of subjects with virologic failure
- To evaluate the kinetics of circulating HCV RNA during treatment and after cessation of treatment
- To evaluate the emergence of viral resistance to LDV and SOF during treatment and after cessation of treatment
- To evaluate the steady-state pharmacokinetics of LDV and SOF, and its metabolites in subjects who are on dialysis for ESRD

The exploratory objectives of this study are:

CCI

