8.6.2. Adverse Events

Clinical and laboratory adverse events will be coded using the Medical Dictionary for Regulatory Activities (MedDRA). System Organ Class (SOC), High-Level Group Term (HLGT), High-Level Term (HLT), Preferred Term (PT), and Lower-Level Term (LLT) will be attached to the clinical database.

Events will be summarized on the basis of the date of onset for the event. A treatment-emergent adverse event will be defined as any adverse event that begins on or after the date of first dose of study drug up to the date of last dose of study drug plus 30 days.

Summaries (number and percentage of subjects) of treatment-emergent adverse events (by SOC, and PT) will be provided by treatment group:

- All AEs
- AEs of Grade 3 or above
- AEs of Grade 2 or above
- All treatment-related AEs
- Treatment-related AEs of Grade 3 or above
- Treatment-related AEs of Grade 2 or above
- All SAEs
- All treatment-related SAEs
- All AEs leading to premature discontinuation of the study drug
- All AEs leading to temporary interruption of the study drug

All AEs collected during the study will be presented in the data listings.

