## 1.2. Study Design

This is a multicenter, open-label Phase 2 study that will evaluate the safety, tolerability, and antiviral efficacy of LDV/SOF in subjects on dialysis for ESRD with genotype 1, 4, 5, or 6 HCV infection.

Approximately 100 subjects with genotype 1, 4, 5, or 6 HCV infection will be enrolled to 1 of 3 groups and will receive treatment with LDV/SOF for 8, 12, or 24 weeks. The treatment group to which subjects are assigned will be determined by genotype, the absence or presence of cirrhosis and whether the subject is treatment naïve or treatment experienced.

Group 1: Treatment naïve genotype 1 subjects without cirrhosis will be treated with LDV/SOF for 8 weeks

Group 2: Treatment experienced genotype 1 subjects and treatment naïve or treatment experienced genotype 4, 5, and 6 subjects without cirrhosis will be treated with LDV/SOF for 12 weeks

Group 3: Subjects with compensated cirrhosis will be treated with LDV/SOF for 24 weeks

The total time to complete all study visits is approximately 52 weeks (42 weeks for those requiring extension of the Screening period):

- 28 days (4 weeks) screening period (or 42 days for extenuating circumstances)
- Up to 24 week treatment period
- Up to 24 week posttreatment period

The schedule of assessments is provided as an appendix to the SAP ([Appendix 1](#)).

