##### **4.2.2. Adherence to Study Drug**

The presumed total number of tablets administered to a subject will be determined by the data collected on the drug accountability CRF using the following formula:

$$\begin{aligned} \text{Total Number of Doses Administered} = \\ (\sum \text{No. of Tablets Dispensed}) - (\sum \text{No. of Tablets returned}) \end{aligned}$$

The level of adherence to the study drug regimen will be assessed based on the total amount of study drug administered relative to the total amount of study drug prescribed at baseline.

The level of adherence will be expressed in percentage using the following formula:

$$\text{Level of Adherence}(\%) = \left( \frac{\text{Total Amount of Study Drug Administered}}{\text{Total Amount of Study Drug Prescribed at baseline}} \right) \times 100$$

Note: If calculated adherence is greater than 100%, the result will be set to 100%.

In this study, the total amount of LDV/SOF prescribed for 8 weeks would require 56 tablets, for 12 weeks would require 84 tablets, and for 24 weeks would require 168 tablets.

Subjects who prematurely discontinue study drug for lack of efficacy (ie, virologic failure) will have the total amount of study drug prescribed calculated up to the first date when virologic failure criteria were met. For virologic failure confirmed by 2 consecutive measurements, the date of the first measurement will be used. If study drug bottles are dispensed on or after the subject first met virologic failure criteria, these bottles will not be included in the calculation of adherence. If a bottle is dispensed and the bottle is returned empty, then the number of tablets returned will be entered as zero. If a bottle is dispensed but not returned (missing), the number of tablets taken from that bottle will be counted as zero.

Descriptive statistics for the level of adherence (n, mean, SD, median, Q1, Q3, minimum, and maximum) with the number and percentage of subjects belonging to adherence categories (eg, {< 80%, ≥ 80 to < 90%, ≥ 90%}) will be provided by treatment group for the Safety Analysis Set. Categorical displays also will be provided for the number of subjects who are at least 80% adherent to their drug regimen (ie, adherence is ≥ 80% for the study drugs).

No inferential statistics will be provided for duration of exposure and adherence to study drug.

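### Adverse event tables by treatment group give only crude percentages over planned windows of 86, 114 and 198 days, so side by side they mix tolerability with length of observation; a Day 56 table would separate the two cheaply.

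*SAP*

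**What the plan says.** Safety is a primary objective, stated per regimen: "To evaluate the safety and tolerability of each treatment regimen" (Protocol 2; repeated in SAP 1.1). The primary safety endpoint is any adverse event leading to permanent discontinuation of study drug (Protocol 8.1.2, SAP 7.1).

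The three regimens differ in length. SAP 1.2 has "Group 1: Treatment naïve genotype 1 subjects without cirrhosis will be treated with LDV/SOF for 8 weeks", then treatment-experienced genotype 1 subjects and "genotype 4, 5, and 6 subjects without cirrhosis will be treated with LDV/SOF for 12 weeks", then "Group 3: Subjects with compensated cirrhosis will be treated with LDV/SOF for 24 weeks". SAP 4.2.2 gives the dosing days through the tablet counts: "for 8 weeks would require 56 tablets, for 12 weeks would require 84 tablets, and for 24 weeks would require 168 tablets".

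An event is treatment-emergent if it starts on or after first dose and "no later than 30 days after permanent discontinuation of study drug" (SAP 7.1.5.1). The planned measure is a count and percentage: "Adverse event summaries will provide the number and percentage of subjects with TEAEs by SOC and PT" (SAP 7.1.6), with each subject counted once per summary. SAP 7.1.6 does not name the table columns. Those come from Protocol 8.6.2, "Summaries (number and percentage of subjects) of treatment-emergent adverse events (by SOC, and PT) will be provided by treatment group", and from SAP 3.2, which groups the Safety Analysis Set by actual treatment received.

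Duration of exposure is summarized separately (SAP 4.2.1) and is not linked to the event counts. Neither document plans a person-time rate, a time-to-event estimate or a common-window table for adverse events.

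**The concern.** A crude percentage with each subject counted once rises with the time over which events are counted, whatever the drug does. Here that time is fixed by group and more than doubles from Group 1 to Group 3. A reader of adjacent columns will look for a duration-related effect, particularly because Protocol 1.5 names high metabolite exposure and falling red cell counts as the risks and expects the data to support dosing recommendations. The planned tables would show such a gradient even if the event rate were identical in all groups, and nothing in the adverse event displays would let the reader tell the two apart.

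**Working it through.** **Plan figures first.** The plan states no adverse event rate or at-risk window to reproduce. The tablet counts reproduce at one tablet daily: 8 × 7 = 56, 12 × 7 = 84, 24 × 7 = 168. The one design figure, an exact 95% CI at most 20% long with 100 subjects, also reproduces (widest at 50 of 100: 39.8% to 60.2%, or 20.3 points), but it does not bear on this point.

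**Windows.** Dosing days plus 30:
- Group 1: 56 + 30 = 86 days
- Group 2: 84 + 30 = 114 days
- Group 3: 168 + 30 = 198 days

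Ratios: 198/86 = 2.30, 114/86 = 1.33, 198/114 = 1.74. With the ±3-day visit window, Group 3 to Group 1 runs from (165 + 30)/(59 + 30) = 2.19 to (171 + 30)/(53 + 30) = 2.42.

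**Effect on percentages.** Assume the same constant first-event rate λ in every group and full planned dosing. Over a window W the expected percentage is 1 − exp(−λW). Eliminating λ gives P3 = 1 − (1 − P1)^(198/86) and P2 = 1 − (1 − P1)^(114/86). Ratios below use unrounded percentages.

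| Group 1 | Group 2 | Group 3 | Group 3 / Group 1 |
|---|---|---|---|
| 5% | 6.6% | 11.1% | 2.23 |
| 10% | 13.0% | 21.5% | 2.15 |
| 20% | 25.6% | 40.2% | 2.01 |
| 30% | 37.7% | 56.0% | 1.87 |
| 50% | 60.1% | 79.7% | 1.59 |
| 80% | 88.2% | 97.5% | 1.22 |
| 90% | 95.3% | 99.5% | 1.11 |

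The ratio has a ceiling of 2.30 for rare events and falls as percentages saturate.

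**Discontinuation events.** These can in practice occur only while dosing, so the windows are about 56, 84 and 168 days, and P3 = 1 − (1 − P1)^(168/56) = 1 − (1 − P1)^3. Group 1 at 5% gives Group 3 at 14.3% (ratio 2.85). At 10% it gives 27.1% (2.71), and at 20%, 48.8% (2.44). The ceiling is 3.0.

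**Levels from the earlier renal study.** Protocol 1.2.2.6 reports 24-week results for sofosbuvir plus ribavirin in severe renal impairment. The regimen and population differ, so using them as Group 3 levels is an assumption.
- SAE, 4/20 = 20%: Group 1 would show 1 − 0.80^(86/198) = 9.2%, ratio 2.17.
- Any AE, (10 + 9)/20 = 95%: Group 1 would show 1 − 0.05^(86/198) = 72.8%, ratio 1.31.
- AE leading to discontinuation of both drugs, 2/20 = 10%: Group 1 would show 1 − 0.90^(1/3) = 3.5%, ratio 2.90.

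**Does a person-time rate settle it?** Only if the rate is roughly constant. Suppose 30% of every group has a first event, spread evenly over the first 56 days (mean 28 days), and none later. The crude percentages are then equal. Person-days to first event or end of window, per subject, are 0.7 × 86 + 0.3 × 28 = 68.6 in Group 1 and 0.7 × 198 + 0.3 × 28 = 147.0 in Group 3. The adjusted rate in Group 3 is 68.6/147.0 = 0.47 times that in Group 1, an artefact in the opposite direction. A percentage through Day 56 gives 30% in both.

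**The case against.** The strongest reply is that no comparison of safety between groups is planned. The objective concerns each regimen and the results are descriptive (SAP 3). For one regimen, the percentage with an event over the full course plus 30 days answers the natural question of risk over that course, and longer exposure is part of a 24-week regimen. This stands: the crude tables are valid and should stay. A reader might infer that the planned analysis is wrong, and the documents do not support that.

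A reader might also infer that Group 3 will look twice as toxic throughout. That is too strong. The doubling applies to Group 3 against Group 1 on less common rows. It shrinks to 1.1 to 1.3 for very common events and cannot exceed 1.74 against Group 2. A high background event rate in dialysis subjects makes the ratio smaller, not larger.

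Nor do the documents support extending the point to an overall adverse event column that depends on the group mix. Protocol 8.6.2 specifies display by treatment group, and neither SAP 3.2 nor SAP 7.1.6 names an overall column for these tables.

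Groups are assigned by cirrhosis, genotype and treatment history, and all of Group 3 has compensated cirrhosis. No adjustment for time removes that confounding.

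Finally, part of the need is already met. Exposure duration is summarized, all events are listed, and hemoglobin and reticulocytes are summarized by visit (SAP 7.2.1), which allows time-matched reading of the red cell risk. That does not extend to the adverse event percentages, including those for the primary safety endpoint.

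**Conclusion.** The point holds as a limited one. The adverse event tables carry only crude percentages over planned windows of 86, 114 and 198 days, or about 56, 84 and 168 on-drug days for discontinuation events. At an equal constant rate, Group 3 would show about twice the Group 1 percentage (1.9 to 2.3) where Group 1 is at or below roughly 30%, 1.1 to 1.3 times for very common events, and up to about 3 times for discontinuation events. The windows follow from the documents. The ratios assume a constant rate and full planned dosing; early clustering of events, or early stopping in Group 3, would lower them.

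No planned number is wrong and no decision rule is affected. The gap is that adjacent group columns cannot separate regimen tolerability from length of observation, and a table from data already collected would do so. This is an inexpensive improvement, not a correction of an error.

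**What to change.** In SAP 7.1.6, keep the crude tables and add the following by treatment group:

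1. The number and percentage of subjects with a first event through Day 56, when all groups are scheduled to be on drug. Cover any AE, Grade 3 or above, SAE, AE leading to discontinuation, and anemia.
2. As a secondary display, for the same categories, first events per 100 person-years at risk with exact 95% CI. Use on-drug person-time for AEs leading to discontinuation. Add a footnote that the rate assumes a roughly constant hazard.
3. A statement that neither display removes confounding from group assignment by cirrhosis, genotype and treatment history.

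A footnote should also count subjects who stop dosing before Day 26. Protocol 7.2.2 collects adverse events for 30 days after last dose, so their non-serious events are not followed to Day 56 (26 + 30 = 56).

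The cost is one or two extra descriptive tables from onset and dosing dates already collected, with no protocol change. The Day 56 table ignores later events, chiefly in Groups 2 and 3; the crude tables still show them.

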## 7.2. Laboratory Evaluations

Laboratory data collected during the study will be analyzed and summarized using both quantitative and qualitative methods. Summaries of laboratory data will be provided for the safety analysis set and will include data collected up to last dose of any study drug plus 30 days for subjects who have permanently discontinued study drug. The analysis will be based on values reported in conventional units. When values are below the limit of quantitation, they will be

listed as such, and the closest imputed value will be used for the purpose of calculating summary statistics. For example, if “< 0.2” was recorded, a value of 0.1 will be used for the purpose of calculating summary statistics; if “< 0.1” was recorded, a value of 0.09 will be used for the purpose of calculating summary statistics.

A by-subject listing for laboratory test results will be provided by subject ID number and visit in chronological order for hematology, serum chemistry, coagulation, and urinalysis separately. Values falling outside of the relevant reference range and/or having a severity grade of 1 or higher on the Gilead Grading Scale for Severity of Adverse Events and Laboratory Abnormalities will be flagged in the data listings, as appropriate.

No inferential statistics will be generated.

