3.2. Visit Schedule

Screening assessments will be completed within 28 days of the Day 1 visit. The screening window can be extended to 42 days for extenuating circumstances with Sponsor approval.

All subjects will complete the following study visits: Screening, Day 1, on-treatment visits at the end of Weeks 2, 4, 6, and 8. Subjects in group 2 and 3 will also complete a Week 12 visit, and subjects in group 3 only, will also complete visit at Weeks 16, 20, and 24. All subjects will complete posttreatment visits at Weeks 4 and 12, after completion of treatment. Subjects who achieve SVR12 will also complete the posttreatment Week 24 visit.

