6.4. Post-treatment Assessments

6.4.1. Posttreatment Week 4 Visit (\pm 5 days): Group 1, Group 2, and Group 3

The following procedures/assessments are to be completed at Posttreatment Week 4:

- Perform complete physical examination, including vital signs
- Assessment of AEs and concomitant medications
- Pregnancy prevention counselling
- Subject completes Health Related Quality of Life Questionnaire: SF-36, CLDQ-HCV, FACIT-F, and WPAI
- Obtain blood samples for:
 - Hematology
 - Chemistry
 - HCV RNA
 - Viral sequencing/phenotyping
 - HIV-1 RNA and CD4 cell count will only be collected and analyzed for HIV co-infected subjects
 - HBV DNA (only in subjects who are HBcAb+ at Screening)
 - Serum β -hCG pregnancy test for females of childbearing potential only

6.4.2. Posttreatment Week 12 Visit (\pm 5 days): Group 1, Group 2 and Group 3

The following procedures/assessments are to be completed at Posttreatment Week 12 and 24:

- Perform complete physical examination, including vital signs
- Assessment of SAEs
- Subject completes Health Related Quality of Life Questionnaire: SF-36, CLDQ-HCV, FACIT-F, and WPAI
- Obtain blood samples for:
 - Hematology
 - Chemistry
 - HCV RNA
 - HBV DNA (only in subjects who are HBcAb+ at Screening)
 - Viral sequencing/phenotyping

6.4.3. Posttreatment Week 24 Visit (\pm 5 Days): Only for Subjects who Achieved SVR12

The following procedures/assessments are to be completed at Posttreatment Week 24:

- Perform complete physical examination, including vital signs
- Assessment of SAEs
- Obtain blood samples for:
 - Hematology
 - Chemistry
 - HCV RNA
 - HBV DNA (only in subjects who are HBcAb+ at Screening)
 - Viral sequencing/phenotyping

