6.9. Procedures and Specifications

6.9.1. Clinical Laboratory Analytes

Hematology: Hematocrit, hemoglobin (Hb), platelet count, red blood cell count (RBC), white blood cell count (WBC) with differential (absolute and percentage) including lymphocytes, monocytes, neutrophils, eosinophils, basophils, reticulocyte count and mean corpuscular volume (MCV).

Coagulation: INR, Prothrombin time (PT), Activated partial thromboplastin time (APTT)

Chemistry: Alanine aminotransferase (ALT/SGPT), aspartate aminotransferase (AST/SGOT), albumin, alkaline phosphatase, creatinine, total bilirubin, direct bilirubin; glucose, potassium, and sodium. Fibrotest® will be done at screening only.

Virological Tests: Serologies for HCV and HBV (HBsAg, HBsAb, and HBcAb). HBV DNA (only in subjects who are HBcAb+ at Screening). Serology testing for HIV (including reflex testing as necessary), HCV RNA will be measured using the COBAS® AmpliPrep/COBAS® TaqMan® HCV Test, v2.0 for Use with the High Pure System, HCV genotype and subtype will be determined using the Siemens VERSANT® HCV Genotype, INNO-LiPA 2.0 Assay. HIV-1 RNA will be measured using the AmpliPrep/COBAS® TaqMan® HIV-1 Test, v2.0. If HIV-1 virologic rebound is confirmed, HIV-1 genotype/phenotype will be determined using the PhenoSense™ Integrase HIV, GeneSeq™ Integrase HIV, PhenoSense™ HIV, GenoSure MG, GeneSeq™ HIV, and PhenoSense GT™.

Gilead reserves the right to use alternate assays for HCV RNA, HIV RNA, HCV genotype, and HIV-1 genotype/phenotype should the above assays become unavailable or the results are not definitive.

IL28B genotype will be determined by polymerase chain reaction (PCR) amplification of the SNP, rs12979860, with sequence specific forward and reverse primers and allele specific fluorescently labeled TaqMan® MGB probes. Gilead reserves the rights to use alternate assays for IL28B determination should the above assay become unavailable.

Pregnancy Tests: Serum β-hCG

Additional Tests: Serum drug screen (for amphetamines, cocaine, methadone, opiates), HbA1c, CD4 T-lymphocyte (absolute count and %)

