8.6. Safety Analysis

Safety will be evaluated by assessment of clinical laboratory tests (including HIV-1 RNA and CD4 T-cell count for HCV/HIV co-infection subjects), physical examinations, vital signs measurements at various time points during the study, and by the documentation of AEs.

All safety data collected on or after the first dose of study drug administration up to 30 days after the last dose of study drug will be summarized by treatment group according to the study drug received.

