Appendix 2. Study Procedures Table

Appendix Table 1. Screening/Baseline/ On-Treatment and Post Treatment Study Visits for Group 1

	Screen	Baseline/Day 1 ^a	On-Treatment Week (± 3 Days)				Post-Treatment Week (± 5 Days)		
			2	4	6	8/ET	4	12	24
Informed Consent	X								
Determine Eligibility	X	X							
Medical History	X								
Physical Examination	X	X				X	X	X	X
Height	X								
Weight	X	X				X			
Vital Signs	X	X	X	X	X	X	X	X	X
12-Lead ECG	X	X				X			
AEs/SAE ^b	X	X	X	X	X	X	X	X ^b	X ^b
Concomitant Medications	X	X	X	X	X	X	X		
Pregnancy Prevention Counseling	X	X		X		X	X		
Health-Related Quality of Life ^c		X				X		X	
Review of Study Medication Compliance			X	X	X	X			
Study Drug Dispensing ^d		X		X					
Hematology, Chemistry	X	X	X	X	X	X	X	X	X
Coagulation Tests	X	X				X			
HCV RNA	X	X	X	X	X	X	X	X	X
Viral Sequencing/Phenotyping ^e		X	X	X	X	X	X	X	X
Sparse PK			X	X	X	X			
Intensive PK ^{g, h}					X ^h	X ^h			

	Screen	Baseline/Day 1 ^a	On-Treatment Week (± 3 Days)				Post-Treatment Week (± 5 Days)		
			2	4	6	8/ET	4	12	24
Hemodialysis PK ^{g,i}					X ⁱ	X ⁱ			
Serum β -hCG Pregnancy Test ^j	X	X		X		X	X		
Serum Drug Screen	X								
HCV & IL28B Genotyping	X								
HCV, HIV, HBV Serology	X								
HBV DNA ^k		X		X		X	X	X	X
HbA1c	X								
Fibrotest [®]	X								
Archive Sample ^f		X				X			
Pharmacogenomic Sample ^f		X							
CD4 Cell Count ^l	X	X		X		X	X		
HIV-1 RNA ^l	X	X		X		X	X		

a Baseline/Day 1 assessments must be performed prior to dosing

b Only SAEs will be collected at post-treatment Weeks 12 and 24.

c Health Related Quality of Life (HRQoL) Surveys (e.g., SF-36, CLDQ-HCV, FACIT-F and WPAI) will be conducted for all subjects where the surveys are available at Day 1, Week 8, ET (if applicable), and posttreatment Week 12.

d The IWRS will provide direction on the specifics of each subject's study drug dispensing

e. Plasma samples will be collected for possible viral resistance testing and other virology studies

f Subjects may opt out of archive/pharmacogenomics sample collection.

g Only for subjects who have provided consent for this sample and testing.

h Intensive PK evaluations will be assessed at the following timepoints: 0 (pre-dose -5 minutes), 0.25, 0.5, 1, 2, 4, 6 ,8, 10, and 12 hours post dose once either on Week 6 or 8, per investigator discretion.

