**Table 3-2. Analysis Windows for Posttreatment HCV RNA, Vital Signs and Safety Laboratory Data**

Nominal FU a Visit	HCV RNA			Vital Signs and Safety Laboratory Data b		
	Nominal FU Day	Lower Limit	Upper Limit	Nominal FU Day	Lower Limit	Upper Limit
FU-4	28	21	69	28	4	30
FU-12	84	70	146	NA	NA	NA
FU-24	168	147	210	NA	NA	NA

a. FU-x visit = posttreatment Week-x follow-up visit.

b. Vital signs and safety labs will only be summarized for the FU-4 visit (up to 30 days after last dose).

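### HBV DNA and ALT are measured in HBcAb+ subjects up to posttreatment Week 24, but no HBV DNA summary is planned and every laboratory and AE table stops at last dose + 30 days

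*SAP*

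**What the plan says.** **Measurement.** Protocol 4.2 excludes only subjects positive for hepatitis B surface antigen, so surface-antigen-negative, HBcAb+ subjects can enrol. For them Protocol 6.4 schedules "HBV DNA (only in subjects who are HBcAb+ at Screening") at posttreatment Weeks 4, 12 and 24. Chemistry, which includes ALT (Protocol 6.9.1), is drawn at the same visits. Week 24 is conditional: "Subjects who achieve SVR12 will also complete the posttreatment Week 24 visit" (Protocol 3.2).

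**Collection of events.** Protocol 7.2.2 ends collection of all AEs 30 days after the last dose, and Protocol 5.4 ends routine concomitant-medication recording at the same point. SAEs continue to the end of follow-up (Protocol 7.2.3). The schedule footnote reads: "Only SAEs will be collected at post-treatment Weeks 12 and 24".

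**Reporting.** Under Protocol 8.6, safety data "up to 30 days after the last dose of study drug will be summarized by treatment group". SAP 7.2 says that laboratory summaries "will include data collected up to last dose of any study drug plus 30 days", and Table 3-2, footnote b, adds: "Vital signs and safety labs will only be summarized for the FU-4 visit (up to 30 days after last dose"). SAP 7.2.2.1 applies the limit to treatment-emergent laboratory abnormalities and SAP 7.1.5.1 to treatment-emergent AEs, on which the SAE tables in 7.1.6 are built. The laboratory listings are specified "for hematology, serum chemistry, coagulation, and urinalysis separately"; HBV DNA is not among those panels.

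**The concern.** By scheduling HBV DNA to Week 24, the protocol treats HBV as something to watch well after treatment. The reporting plan does not follow it there. Take an HBcAb+ subject whose HBV DNA and ALT rise at posttreatment Week 12 without the event being judged serious. Both results are in the database, but no planned table can show them. A reader of the safety tables could not tell whether any late rise occurred. The answer would have to be assembled by hand from listings, without a prespecified definition of what counts as a rise. Safety and tolerability is a primary objective, and this is a risk for which the trial draws dedicated samples.

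**Working it through.** The documents state no figure for this point, so there is none to reproduce. The check compares the visit schedule with the reporting limits.

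**1. Scheduled visits against the 30-day limit.** Nominal day = 7 × week; the permitted window is ±5 days (Protocol 6.4).

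| Posttreatment visit | Nominal day | Permitted days | Permitted days at or before day 30 |
|---|---|---|---|
| Week 4 | 28 | 23–33 | 8 of 11 |
| Week 12 | 84 | 79–89 | 0 of 11 |
| Week 24 (SVR12 only) | 168 | 163–173 | 0 of 11 |

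Two of three posttreatment assessments always fall after the limit. For subjects without SVR12, who end at Week 12, it is one of two. A permitted Week 4 visit on days 31–33 also drops out of the laboratory summaries.

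**2. Follow-up time after the limit.** Followed to Week 24: 168 − 30 = 138 days, and 138/168 = 82%. Ending at Week 12: 84 − 30 = 54 days, and 54/84 = 64%. These are shares of calendar time, not of events.

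**3. What each result can reach in the report.**

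- *HBV DNA.* It is absent from the analytes summarized in SAP 7.2.1 and from the panels listed in 7.2. SAP 7.6 contains only a pregnancy listing. The grading scale in Protocol Appendix 3 has no HBV DNA row, so a rise cannot become a graded abnormality even on treatment. In the readable SAP, HBV DNA appears only in the appended schedule. The general rule in SAP 3, that collected data are listed by subject, is the only one that reaches it. No definition of an HBV DNA rise is given.
- *ALT.* It is summarized and graded to day 30. SAP Table 3-2 gives HCV RNA windows for FU-12 (days 70–146) and FU-24 (days 147–210) but marks safety laboratory data as not applicable at both. Later values appear in the chemistry listing, flagged when out of range or graded.
- *Non-serious AE first found at Week 12 or 24.* This is outside the collection period and outside the tables.
- *SAE starting after day 30.* It is collected and listed, but does not meet the treatment-emergent definition and so is not in the SAE tables.
- *Death.* All deaths are summarized, treatment emergent or not (SAP 7.1.6).

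**The case against.** The strongest reply is that a 30-day window is a normal convention, that both documents apply it consistently, and that late information is not lost. Much of this stands.

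- A reader might infer that all AE collection stops at day 30. It does not. SAEs are collected throughout, and Protocol 7.1.2 lets an investigator classify a medically important event as serious without hospitalization.
- A reader might infer that an HBV antiviral started late would go unrecorded. That is not established. Medication given for an SAE must be recorded (Protocol 7.2.4), and unscheduled visits collect AEs and concomitant medications with no stated time limit (Protocol 6.6). The latter sits uneasily with Protocol 5.4 and 7.2.2, but it is there.
- A reader might infer that a late flare would be invisible. Late ALT abnormalities are listed and flagged (Protocol 8.6.3, SAP 7.2), and deaths are counted.
- SAP 7.2.2.2 has a general sentence on summarizing categorical laboratory results at scheduled visits. It does not name HBV DNA and falls under the 30-day limit of SAP 7.2.

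What the reply does not meet is the absence of any table for the late HBV DNA and ALT results. A listing without a definition, and without HBV DNA and ALT set together, does not answer the question the samples were drawn to answer. Keeping the 30-day window for general safety is compatible with one separate display.

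**Conclusion.** The gap is real and confined to reporting. Late HBV DNA and ALT results in HBcAb+ subjects are measured and at most listed, and late SAEs are listed but not tabulated. Two of three scheduled posttreatment HBV DNA/ALT assessments (one of two for subjects ending at Week 12) fall outside every laboratory summary. HBV DNA itself has no named summary at any visit.

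Two stronger readings are not supported. One is that the primary safety question would be answered wrongly. The primary safety endpoint is AEs leading to permanent discontinuation of study drug (Protocol 8.1.2, SAP 7.1), and an event first arising at posttreatment Week 12 cannot change it. The other is that 82% of follow-up days, or an assumed HBcAb+ share of the 100 subjects, measures the harm. The former is time and the latter counts people tested; neither counts late reactivations. The documents give neither the HBcAb+ share nor a reactivation rate, so no number of affected subjects or missed events follows.

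The conclusion rests on the readable text. A redacted section could hold an HBV analysis, but nothing visible points to one. This is an inexpensive improvement to the safety report, not a threat to the main results.

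**What to change.** In SAP 7.6, add for HBcAb+ subjects a table and a listing of HBV DNA with same-visit ALT at every scheduled HBV DNA visit, from Day 1 through the last posttreatment visit. Include the number of subjects whose HBV DNA goes from not detected at Day 1 to quantifiable, or rises from Day 1 by a log10 threshold fixed before database finalization. The threshold defines a display only and is not a treatment rule. State the exception to the 30-day limit in SAP 7.2 and in Table 3-2, footnote b. Add a separate count of SAEs starting after last dose + 30 days. Keep the 30-day window for all other safety summaries.

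This needs SAP wording and a small amount of programming on data already collected, with no new visit or sample. The cost is one extra table, and events outside the standard window that must be shown separately so that they are not mixed with treatment-emergent ones.

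Optionally, if the protocol is amended anyway, reconcile Protocol 5.4, 6.4, 6.6 and 7.2.2 with the Concomitant Medications row and footnote b of the schedule, so that non-serious HBV-related AEs and related medications found at posttreatment Weeks 12 and 24 are recorded. These places have to change together, and the change needs ethics committee approval under Protocol 9.2.1, so it is secondary to the SAP change.
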